This proposal unites neuroimagers, experts in conducting and analyzing human PET studies with behavioral scientists, experts in developing and testing treatments for alcoholism. We will conduct the first-ever *in vivo* PET imaging study of KOR and NTX occupancy in two cohorts of HD (18 FHP and 18 FHN) and relate our imaging findings to FH and alterations of drinking behavior by NTX in the ADP. Through this work, we will advance our understanding of (a) the degree of involvement of the kappa system in reducing drinking in humans by NTX, (b) the contribution of FH to this relationship, and (c) refine the use of a new PET imaging tracer. In so doing, we will inform the development of future targeted pharmacotherapies for alcoholism and lay the groundwork for other important investigations into the KOR/dynorphin system *in vivo*.

Primary (P), Secondary (S), and Auxiliary (A) Specific Aims:

- P1. **Occupancy of KOR by NTX and drinking:** To determine the degree to which occupancy of KORs by a 100 mg/day dose of NTX mediates (influences the strength of) responsivity to NTX treatment in all heavy drinkers. It is expected that KOR occupancy will significantly mediate the relationship between NTX treatment and responsivity. „Responsivity“, measured via ADP, is the change in number of drinks consumed at the baseline ADP vs. NTX ADP.
- P2. **Family History of Alcoholism as a moderator:** To determine whether the relationship between NTX responsivity and occupancy of KOR is different in FHP vs. FHN heavy drinkers.
- P3. To determine if baseline KOR availability differs between heavy drinkers and healthy control socialdrinkers

S1. **Baseline KOR differences**

- a. To determine if baseline levels of KOR differ between FHP and FHN heavy drinkers.
- b. To determine if baseline KOR level is related to either baseline drinking or responsivity to NTX.

S2. **Identify and validate a reference region** (area devoid of specific binding) for our new KOR tracer. A reference region would simplify PET analysis.

S3. **Optimize the scan duration** for clinical populations being imaged with the new KOR tracer.

Shorter scans would increase compliance and decrease discomfort to subjects.

A1. **Relationship to other behavioral measures:** To determine if occupancy of KORs is related to measures of alcohol craving, stimulation or sedation, assessed in the ADP.

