Our project will investigate a provocative finding in alcohol treatment research [3]. Namely, that FH of alcoholism may influence (or be a marker of an underlying trait that influences) the response of heavy drinkers (HD) to NTX. Simply put, not every HD responds favorably to NTX but lower levels of drinking can be achieved and risk of relapse is diminished in some. It is essential for clinical treatment and future drug development to understand how NTX works. Preclinical results have implicated kappa in *changes* in alcohol drinking, but the directionality of these changes are complex. We propose that the differential efficacy of naltrexone may be related to differences in occupancy of kappa opioid receptors by naltrexone. This translational project will test this hypothesis. The results of this project could not only help maximize treatment effectiveness of naltrexone but also result in identification of new medication treatment targets for more optimal reduction of alcohol drinking.

3. Research Plan: Provide an orderly scientific description of the study design and research procedures as they directly affect the subjects.

A total of 56 HD subjects will be tested; equal numbers of FHP and FHN subjects will be recruited. Data from the first year's subjects ("initial cohort" perhaps specify how many will be used for this purpose) will be analyzed prior to scanning the remaining subjects in order to address aims S2 and S3 (identification and validation of a reference region; reduction in scan duration) which are addressed below in PET methods.

Study design: Because we are interested in investigating the implications of baseline KOR, as well as Occupancy of KOR by NTX, we must perform 2 PET scans on each subject; one at

baseline and one following 5-11 days of NTX pretreatment. Similarly, because we are interested in relating responsivity to occupancy of KOR by NTX we must make two assessments of drinking behavior using the ADP; one at baseline the day before or after the first PET scan and one following 5-11 days of treatment with NTX. The post PET scan and post ADP will ideally take place on Day 6 or Day 7 of medication, but we will allow up to 11 days of medication for scheduling issues and the possibility that the appointments will be within this time frame. All

In designing the study, we had to balance various competing interests and we provide justifications below:

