Analysis of Initial Cohort: Data from the first 6 FHP and 6 FHN subjects scanned in year one of the project (24 scans total) will be analyzed to determine whether or not a reference region exists for [11C]LY2795050 ([11C]-PKAB) and whether or not the scan duration can be shortened without loss of precision of the data. To be sure that a reference tissue model is appropriate in our study, two findings are required. The V_T of the putative reference region must be unchanged by blocking and the endpoint, BP_{ND} , estimated by the reference region method must agree with the BP_{ND} calculated using an AIF. If the BP_{ND} values from 2T and SRTM continue to show excellent agreement, as applied to *both* baseline and NTX scans, then we may choose to discontinue arterial sampling thereafter and rely solely on a reference region model for analysis. After a preliminary analysis of the initial cohort, we will determine the acquisition protocol for the remaining 24 subjects.

Modeling of PET data to yield BP in regions of interest and parametric images

1. Standard kinetic modeling approaches: With plasma input function measurements in hand, we can compare multiple standard methods of estimating our desired endpoints (BP_{ND} at baseline and difference in BP_{ND} from baseline to NTX) to determine the best model or technique [52] that yields the lowest variance in the estimates. Tentatively based on preliminary data, we expect to use the cerebellum as the reference region for reference region methods but we will continue to investigate the possibility of another (better) reference region.

2. Measuring occupancy does not depend on displacement, time of day:

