- l) Psychophysiological Measures: These will include heart rate and blood pressure monitored

using a Critikon Dinamap while skin temperature will be measured using Yellow Springs Instruments 4600 precision thermometer. The cuff of the Dinamap will be on the subject's dominant arm while the probe of will be attached to the middle finger of the subject's non-dominant arm. These data will be further used to examine the safety of using the medication combination during alcohol self-administration.

1) **Cold Pressor Task** (Edens & Gil, 1995): To evaluate the ability of participants to deal with a physiological stressor and to examine pain thresholds in relation to medication effects and drinking behavior. Subjects will be informed that the experimenters are investigating the body's physiological response to cold water during nicotine withdrawal. Subjects will be asked to immerse their right arms into ice water maintained at 3-4°C. Subjects are asked to raise their left hand when they begin to feel pain (pain threshold) and to remove their hand from the water when they can no longer tolerate the pain (pain tolerance). While their hand is immersed in water subjects are also asked to rate their pain on an analog scale of 0-100.

3. **Statistical Considerations:** Describe the statistical analyses that support the study design. Outcomes for this study will be collected using scannable forms (Teleforms). The scanned forms will be processed through the Teleforms software and exported to a database on a secure computer. Error checking and data validation will occur weekly and any problems will be queried and resolved immediately. Drs. [name] will receive monthly data quality reports to check for completeness and accuracy of key demographic and prognostic variables, as well as rates of recruitment, retention, and follow-up. Statistical tests will be conducted using SAS v9.1 and SPSS v16 (or later) and will be performed at 2-tailed alpha level of 0.05

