Auxiliary Aim 1. Kappa and behavioral indicators relevant for alcoholism. This aim will examine the correlations between occupancy of KOR and alcohol craving, stimulation and sedation. A series of Spearman rank-order and Pearson correlation analyses will be conducted for this aim.

Power analysis: The sample size was based on the power calculations for the hypotheses of (a) reduced drinking in the NTX 100 condition, and (b) power to detect an interaction by FH. Power calculations were generated using G*Power software Version 3.0 [55]. Effect sizes were estimated based on the preliminary FH and NTX effects on drinking behavior in the ADP described in [6] and in our preliminary studies. The effect size for the effect of FH is .91. To detect this effect size at $\alpha=.05$ with 80% power, a total of 16 participants would be required for each arm. Therefore the proposed sample size of $n=18$ per arm would be sufficient to detect differences in drinking between FHP and FHN at the 100 mg dose of naltrexone.

SECTION VI: RESEARCH INVOLVING DRUGS, DEVICES, BIOLOGICS & PLACEBOS

Are there any investigational devices used or investigational procedures performed in a YNHH Operating Room? Yes No *If Yes, please be aware of the following requirements:*

- a. A YNHH OR New Product/Trial Request Form must be completed. Please contact the OR Materials Manager, [name], at [contact] for more information on this requirement;
- b. Your request must be reviewed and approved by the Operating Room New Technology Committee before patients may be scheduled; and
- c. The notice of approval from the OR New Technology Committee must be submitted to the HIC for the protocol file.

1. **Identification of Drug, Device or Biologic:** What is (are) the **name(s)** of the drug(s), device(s) or biologic(s) being used? Identify whether FDA approval has been granted and for what indication(s).
Naltrexone is an FDA approved drug that is used in the treatment of alcoholism and opioid addiction.
[C-11]LY2795050 ([C-11]PKAB) PET radiotracer to image kappa opioid receptor, Production of [C-11]LY2795050 ([C-11]PKAB) will be performed with the permission of Yale-New Haven Hospital RDRC

All protocols which utilize a drug, device or biologic **not** approved by, but regulated by, the FDA must provide the following information: **Not applicable to this research project**

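### The stated 16 per arm for 80% power is a one-sided figure. At the plan's two-sided 0.05 the requirement is 20 per arm, 18 per arm gives 76%, and 18 per arm does not match the 56-subject target.

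*Combined protocol and SAP*

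**What the plan says.** The opening of Statistical Considerations sets the error rate: tests "will be performed at 2-tailed alpha level of 0.05".

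The Power analysis paragraph of that section names two bases for the sample size: reduced drinking on naltrexone, and an interaction with family history. It gives one calculation. "The effect size for the effect of FH is .91". "To detect this effect size at $\alpha=.05$ with 80% power", it says, "a total of 16 participants would be required for each arm". It concludes that 18 per arm "would be sufficient to detect differences in drinking between FHP and FHN at the 100 mg dose of naltrexone". It names G*Power 3.0 as the software, but it does not name the test, the effect-size metric or the number of tails.

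The number of heavy drinkers differs between sections:

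- **36.** The statement of purpose describes "two cohorts of HD (18 FHP and 18 FHN". The power paragraph has 18 per arm. In PET Methods, Analysis of Initial Cohort, 6 FHP and 6 FHN subjects are analysed first, and then "we will determine the acquisition protocol for the remaining 24 subjects" (12 + 24 = 36).
- **56.** The Research Plan says "A total of 56 HD subjects will be tested; equal numbers of FHP and FHN subjects will be recruited". Targeted Enrollment, Recruitment Procedures and Subject Population also give 56.

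**The concern.** Two things looked wrong. First, 16 per arm is small for a two-sided two-sample comparison at d = 0.91 with 80% power, which suggests that a one-sided calculation was used to justify a two-sided analysis. If so, the statement that 18 per arm is enough fails the plan's own 80% criterion. A one-sided test is declared nowhere. It would also sit badly with a plan that expects FHP and FHN drinkers to respond in opposite directions.

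Second, the paragraph justifies 18 per arm, while the enrolment target implies 28. A reader cannot tell which analysable number the power statement supports.

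This is the only sample-size justification in the plan. If 36 is the true analysable number, the Type II error for this contrast is about 24%, not the 20% or less that the text implies. The naltrexone effect, named as the other basis for the sample size, has no figure at all.

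**Working it through.** **Inputs**

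- Effect size 0.91, alpha 0.05, power 80%, stated requirement 16 per arm, proposed 18 per arm: Power analysis paragraph.
- Two-sided testing: opening of Statistical Considerations.
- 56 heavy drinkers in equal groups, so 28 per arm: Research Plan.
- Assumption: 0.91 is Cohen's d for two independent groups of equal size, compared by a t-test. The documents do not name the metric or the test.

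**Formula.** With n per arm, degrees of freedom are 2n − 2 and the noncentrality parameter is d × √(n/2). Power is the probability that a noncentral t variable with these parameters exceeds the critical value t(1 − α) for one side, or t(1 − α/2) for two sides. In the two-sided case the opposite tail is negligible.

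**Reproducing the plan's figure (one-sided 0.05)**

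- n = 16: df = 30, noncentrality = 0.91 × √8 = 2.574, critical t = 1.697, power 80.8%.
- n = 15: power 78.4%.

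The smallest n that reaches 80% is 16 (unrounded 15.65), which is the stated number.

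**The same inputs at the plan's two-sided 0.05**

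| n per arm | df | Noncentrality | Critical t | Power |
|---|---|---|---|---|
| 16 | 30 | 2.574 | 2.042 | 70.2% |
| 18 | 34 | 2.730 | 2.032 | 75.6% |
| 19 | 36 | 2.805 | 2.028 | 77.9% |
| 20 | 38 | 2.878 | 2.024 | 80.1% |
| 28 | 54 | 3.405 | 2.005 | 91.7% |

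The requirement is 20 per arm (unrounded 19.96). A normal approximation gives 19, and 77.9% power at 18 per arm, so the conclusion does not depend on the exact method. The smallest effect detectable with 80% two-sided power is 0.96 SD at 18 per arm, which is larger than the assumed 0.91. At 28 per arm it is 0.76 SD.

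**Other two-sided readings of .91.** None gives 16 per arm:

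- Mann-Whitney test: 21 to 24 per arm.
- Paired t-test: 12 subjects.
- ANOVA with f = .91: 12 in total.
- Repeated-measures interaction with f = .455: 12 in total at correlation 0.5, 22 in total at correlation 0.

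**The heavy-drinker number.** 18 + 18 = 36 and 12 + 24 = 36, against 56 = 28 + 28. If 36 were completers out of 56 enrolled, the implied loss would be 20/56 = 36%. No such rate is stated. The enrolment section expects 66 subjects (56 heavy drinkers and 10 controls) to complete some or all interventions.

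**The case against.** The strongest reply has three parts.

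**The test is not named.** Each subject has a baseline and a naltrexone drinking session, so the comparison could be adjusted for baseline drinking. If 0.91 were a between-group d before adjustment, the effective d becomes 0.91/√(1 − r²), where r is the baseline correlation. At r = 0.46 that is 1.025, and 16 per arm then gives 80.0% two-sided power (df = 29). At r = 0.35, 18 per arm gives 80.8%. This shows that a one-sided t-test is the best-fitting explanation of 16, not the only conceivable one. It does not rescue the text: the plan states no such correlation and specifies no baseline-adjusted model.

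**The shortfall depends on which number is current.** If 56 is the live target, 80% power needs 40 evaluable subjects, so up to 16 of 56 (29%) could be lost. The study may well be adequately powered for this contrast. That point stands. The paragraph is still wrong, because it justifies 18 per arm with a figure from a different test.

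**36 and 56 could be completers and enrolled.** Subjects may be discontinued for not drinking at the first session, and payments are structured against drop-out, so losses are foreseen. But no sentence makes the link, and the Research Plan says that all 56 are to be tested.

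**Conclusion.** The concern holds. Under the plan's two-sided 0.05, both the requirement of 16 per arm and the sufficiency of 18 per arm are wrong. The requirement is 20 per arm, and 18 per arm gives 75.6% power, 4.4 points below the 80% claimed. This rests on reading .91 as Cohen's d for two independent groups without baseline adjustment, which the exact one-sided match at 16 supports.

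The conflict between 36 and 56 heavy drinkers needs no assumption. The practical consequence depends on how it is resolved: a Type II error of 24% if 18 per group are analysed, or 8% if 28 per group are.

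**What to change.** 1. Restate the calculation with its test, metric and sidedness. For example: a two-sample t-test at two-sided alpha 0.05 with Cohen's d = 0.91 requires 20 evaluable subjects per FH group for 80% power. If a baseline-adjusted analysis was intended, specify it and give the assumed correlation with its source.
2. Use one heavy-drinker number in the statement of purpose, Targeted Enrollment, Research Plan, Analysis of Initial Cohort, Power analysis, Recruitment Procedures and Subject Population. If 56 is the number enrolled and a smaller number is expected to be evaluable, state both and the attrition assumption that joins them.
3. Report the matching power: 92% for 28 evaluable per group, or 76% (detectable effect 0.96 SD) for 18. Correct the count of subjects remaining after the initial 12. With 56 in total it would be 44.
4. Give a power figure for the naltrexone effect on drinking, or stop citing it as a basis for the sample size.

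The cost is wording only if 56 is confirmed or if 76% is accepted. If 36 is the intended number and 80% power is to be kept, 4 more evaluable subjects are needed (40 instead of 36), which is still below the 56 already planned.

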A total of 4 human subjects (2 M, 2 F, 73 ± 16 kg) underwent whole body dynamic PET scanning on the Siemens ECAT HR+ scanner following iv bolus injection of [¹¹C]PKAB

(injected activity = 282 ± 68 MBq). Subjects were scanned for 150 to 170 min in a sequence of 12 or 14 passes with 8, 9 or 11 bed positions according to their sizes, covering each subject from top of the head to mid-thigh. Scans were reconstructed and visually inspected for organ activity concentrations exceeding background level. Included organs were liver, kidneys, urinary bladder contents, heart, gallbladder, brain, spleen, thyroids, gonads and red marrow (femur). Regions of interest were drawn on these organs and mean activity values computed in order to form time activity curves of activity concentration (kBq/cm^3).

Within-pass decay correction was removed to reflect actual activity in each organ, and cumulated activity ($\text{Bq}\cdot\text{hr}/\text{cm}^3$) computed as trapezoid sums for data from the scan plus physical decay for the tail portions after the scan period. These were multiplied by the organ volumes of a standard 70 kg reference mathematical phantom, normalized by subject mass / 70 kg and then normalized to injected activity to obtain organ residence times (also called N), (hr). These were entered into Olinda software to obtain absorbed doses in all organs. Electron doses to the stomach were adjusted to reflect the fact that activity was observed in stomach wall rather than contents.

Absorbed doses derived from the 70 kg reference man phantom were expressed as mean \pm standard deviation across the 4 subjects. Under RDRC exposure limits as specified in CFR 361.1, (For single study, 5 rem per organ or 3 rem to selected organs undergoing rapid cell division, whichever is less) gallbladder is the dose-limiting organ with single study dose of 26 mCi. Applied to the 55 kg adult female phantom (Table 2), gallbladder is still the critical organ, with single study dose limit of 23 mCi.

PET Imaging Results –Imaging of KOR Sites

Introduction

The preliminary data in this section represent our initial experience with the new PET tracer [^{11}C]LY2795050 ([C-11]-PKAB) in humans and monkeys. A number of opioid receptor radiotracers are currently available for PET imaging in humans: [^{11}C]carfentanil(μ -specific), [^{11}C]/[^{18}F]diprenorphine (nonspecific), [^{11}C]buprenorphine (nonspecific), [^{18}F]cyclofoxy (μ , κ), and [^{11}C]methylnaltrindole (δ) [33]. None of these existing tracers is selective for KOR. So far, the results with [^{11}C]LY2795050 ([C-11]-PKAB) suggest that it is taken up consistent with the known distribution of KOR [34-36]; It also appears to have good contrast to background properties, good test/retest reproducibility, and there may be a reference region with little to no KOR.

[figure not shown]

Figure 2. Top row: MRI images of an individual subject. Middle row: 0-10 min summed PET image. Bottom: 60-120 min summed PET image. Left column: axial slice; middle column: coronal slice; right column: sagittal slice. The amygdala is bright on all three views at late time. The cingulate cortex is apparent on the coronal image at late time.

Occupancy of KOR by NTX – or simply “occupancy” - is measured as a percentage change in BP_{ND} from the baseline condition to the drug condition (in our case, a week of NTX treatment). If we assume that neither the K_D nor the f_{ND} of the tracer change in an individual between scans, then occupancy can be seen to be the fractional change in available receptors due to the drug.

Total Volume of Distribution, V_T , is a related concept to BP. V_T is the equilibrium ratio of the concentration of parent tracer in tissue to parent tracer in plasma.

b. In vitro results

Radioligand competition assays were conducted to assess the *in vitro* binding affinities of LY2795050 to opioid receptors. LY2795050 is a KOR antagonist and displays high binding affinity and great selectivity to KOR *in vitro* ($K_i = 1.37, 87.3, \text{ and } 475 \text{ nM}$, respectively, for kappa, mu, and delta receptors) [38].

[figure not shown]
[figure not shown]
c. Test/retest imaging in humans

Seven healthy volunteers, age = 26 ± 6 (5 males and 2 females), participated in a test-retest study of [^{11}C]LY2795050 ([C-11]-PKAB), an antagonist PET radiotracer for the KOR. Each subject received two bolus injections of up to 20 mCi of radioactivity and mass dose of $\leq 10 \mu\text{g}$ for each injection. The injected activity dose was $13.0 \pm 4.6 \text{ mCi}$, specific activity was $0.59 \pm 0.22 \text{ mCi/nmol}$ at time of injection, and injection mass was $8.8 \pm 1.2 \mu\text{g}$ across all subjects. Arterial (plasma) input function (AIF) curves were prepared from arterial samples taken during the study. Metabolite fraction was applied to yield an input curve for the native tracer only. BP_{ND} throughout the brain (calculated two different ways) was used as the study endpoint. Further details of our standard image processing methods are given below under „PET methods”.

d. Distribution of [^{11}C]LY2795050 ([C-11]-PKAB) in the brain

Figure 2 shows the early- and late-time distributions of [^{11}C]LY2795050 ([C-11]-PKAB) in the brain. The early image is an average of the 0-10 min data (middle row); it reflects initial entry into the brain via blood flow. The late image is an average of the 60-120 min data (bottom row) and reflects preferential retention of the tracer by brain regions containing specific binding sites for the tracer. Rank order of activity uptake was as follows: amygdala (AMY) > cingulate cortex (CIN) > globus pallidus (PAL) ~ putamen (PUT) > temporal cortex (TEM) ~ frontal cortex (FRO) > hippocampus (HYP) ~ caudate (CAU) > cerebellum (CER). The distribution of tracer at late time agrees with the known distribution of kappa receptors in the brain [34-36].

e. Time-activity curves: for use with kinetic models

Estimates of kinetic parameters require regional tracer concentration values over time. Automatic regions-of-interest (ROI) were applied (see PET methods) to the dynamic emission images to generate time-activity curves (TACs) in 13 ROI's. The time-activity curves (TAC) were fitted to the 4-parameter, 2-tissue compartment model (2T) using the metabolite-corrected input function. Examples of fitted TACs are shown in Figure 3. All of the regions were fit well by the 2T model. The rapid efflux from the cerebellum compared to the other regions suggests that the cerebellum has little to no specific binding and is therefore a possible reference

region. However, the definitive identification of a reference region must be based on displacement experiments.

f. Regional distribution of desired endpoint: KOR at baseline (BP_{ND})

We computed BP_{ND} in each ROI two ways. One method requires the use of AIF and the other does not. From the fits of the TAC data via 2T model with AIF, we calculated BP_{ND} as the relative difference in volumes of distribution between the target ROI and the putative reference region, in this case, cerebellum: $(V_T(ROI) - V_T(CER)) / V_T(CER)$. BP_{ND} was also computed using the Simplified Reference Tissue Model (SRTM) using the cerebellum as the reference region. The regional distribution of BP_{ND} based on 2T and SRTM is shown in Figure 4. Figure 4 shows that the methods are in close agreement and the variability, by region, across the cohort is small.

[figure not shown]

Figure 5 **a.** Effect of pre-block with unlabeled KOR antagonist drug. Baseline TACs for cerebellum (CER), caudate (CAU), and frontal cortex (FRO) (solid circles, open circles, diamond, all in red). Curves after pre-block (blue) all show reduced specific binding and are nearly indistinguishable from CER at baseline. Curves are from one animal and are normalized to injected activity dose. **b.** BP_{ND} is reduced dose-dependently according to dose of specific KOR antagonist in both CAU and FRO region.

g. Pre-blocking of [11C]LY2795050 ([C-11]-PKAB): can we detect drug occupancy at kappa sites?

We can verify that uptake and retention of [11C]LY2795050 ([C-11]-PKAB) is due to specific binding to KOR by looking at pre-blocking studies with well-characterized (unlabeled) drugs. Pre-blocking studies were performed in 3 rhesus monkeys. The experiments were similar to what is being proposed herein to measure occupancy of KOR by NTX. In the preliminary studies, rhesus monkeys were given iv, 1mg/kg naloxone, a non-selective KOR antagonist, or varying doses of LY2456302, a selective kappa antagonist developed by an industry partner. Example results for the blocking studies are shown in two parts of Figure 5. Figure 5a: At baseline, regions such as CAU and FRO appear to have more uptake than CER. Under pre-block with the specific KOR antagonist, TACs for two target regions (CAU and FRO) are nearly identical to the putative reference region (CER) in the unblocked case because they reflect only (the same) non-displaceable binding. The data from these two experiments on the same animal have been normalized by injected activity. The behavior of the regions shown is typical. These data are suggestive, but not definitive proof that CER is a valid reference region (See "SRTM vs. 2T", immediately below for criteria). Further evidence of specific binding in CAU and FRO is shown in 5b. BP_{ND} declines in a dose-dependent manner as the specific KOR antagonist dose is increased from low to high.

[figure not shown]
[figure not shown]

Figure 6. Percent change in BP_{ND} from test to retest scans for both 2T (blue bars) and SRTM (red bars) models. Each region is based on the average of 7 subjects. Test/retest variability is actually slightly better for SRTM estimates than for 2T.

h. SRTM vs 2T: Can we use a reference region model?

A reference region model such as SRTM has a number of practical advantages. Its use obviates the need for arterial sampling, thus decreasing the risk to the patient and simplifying the PET experiment. Figure 4 shows that estimation of BP_{ND} via SRTM and 2T is in good agreement and that use of the reference region method would be justified. In this case, CER was used as the reference region. The correlation based on all regions over all subjects was $BP_{ND}(SRTM) = 1.01 * BP_{ND}(2T)$, $R^2 = 0.98$,

which confirms near-perfect agreement. Note: this agreement between the 2T and SRTM does not *validate* the CER as a true reference region. It indicates a valuable fact: the two estimates of BP_{ND} are consistent (they might both be biased for different reasons). For many purposes, consistency may be sufficient to argue for adoption of the SRTM or other reference method. For the reference region to be validated (i.e., shown to be devoid of specific binding), we must also show that V_T of the region does not change in the presence of a pre-blocking drug such as NTX.

- i. Percent change between „test“ and „retest“ scans: How small an effect can we detect?

Small test/retest variability is essential for us to be able to detect small differences between conditions. For each subject, the test-retest variability was measured by computing the ratio of the difference between binding potentials to their means:

$$\frac{100 * (BP_{ND}(TEST) - BP_{ND}(RETEST))}{[\frac{1}{2} (BP_{ND}(TEST) + BP_{ND}(RETEST))]}$$

The mean test-retest variability indices were 8.2% (2T) and 7.2% (SRTM) indicating that BP_{ND} values increased during the retest scan (conducted in the afternoon of the same day) compared to the test scan, across all regions. Figure 6 shows the test/retest comparison as an average value over subjects for all regions.

- j. 90 min vs 120 min results: Can we shorten the scan?

A 1 ½ hr PET scan is slightly less burdensome for the subject than a 2 hr scan and given the fairly rapid kinetics of the tracer, it seems worth considering the shorter scan. Therefore, we compared results of BP_{ND} estimates from the SRTM model using the full 120 min worth of scan data and using only 90 minutes of data. The answers were nearly identical. The correlation plot between the two families of estimates is shown in Figure 7. We conclude from this exercise that we need only to scan for 90 minutes in each scan session. A shorter scan time could improve subject compliance.

- k. BP_{ND} images

One advantage of having a kinetically well-behaved tracer, such as [^{11}C]-LY2795050 ([C-11]-PKAB), with sufficient signal to noise in the TACs for each pixel, is that we can produce pixel-by-pixel parametric images of BP_{ND} . Figure 8 shows BP_{ND} (created with two variants of the SRTM model) for one of the subjects in our test/retest cohort. The middle row in the figure presents three canonical views of the BP_{ND} estimated by SRTM; the bottom row repeats the same views of BP_{ND} images estimated via SRTM2 which imposes a constraint that the apparent efflux rate parameter, k_2 be the same at each voxel. The constraint has the effect of reducing the variance in the image which may further aid our ability to detect slight differences between patient populations or conditions. The images show that there is discernible specific binding of tracer in cortical areas and maximal specific binding in the amygdala and cingulate cortex.

Summary: As we have shown above, we have developed and validated a specific KOR ligand that has high specificity and sensitivity and that can be combined with our established ADP to evaluate the hypotheses that are central to the current proposal.

[figure not shown]

Figure 8. Top row: MRI images (axial, coronal, sagittal) of individual subject. Middle row: Corresponding BP_{ND} images estimated using SRTM. Bottom: Corresponding BP_{ND} images estimated using SRTM2. They are slightly less noisy than SRTM, as would be expected.

3. **Source:** a) Identify the source of the drug, device or biologic to be used.
All study medications (naltrexone) will be purchased from appropriate vendors through the Investigational Pharmacy of YNHH.

Production of [C-11]LY2795050 ([C-11]PKAB) will be performed with the permission of Yale-New Haven Hospital RDRC

- b) Is the drug or device provided free of charge? Yes No
If yes, by whom?

4. **Preparation and Use:** Describe the method of preparation, storage, stability information, and for parenteral products, method of sterilization and method of testing sterility and pyrogenicity.

The starting material for the production of [C-11]PKAB / [C-11]LY2795050 will be provided by Eli Lilly and company. Manufacturing of [C-11]LY2795050 ([C-11]PKAB) will be carried out at the Yale PET Center.

[¹¹C]Carbon dioxide is produced by bombardment of a target containing a mixture of nitrogen and 0.5 – 1% oxygen with accelerated protons. [¹¹C]CO₂ is then converted to [¹¹C]HCN using an automated chemistry device from GE Medical Systems. Reaction of [¹¹C]HCN with the iodo precursor LY2806578 under Pd(0)-catalyzed conditions provides the radiolabeled benzonitrile intermediate [C-11]LY2893110, which is hydrolyzed under basic conditions and in the presence of hydrogen peroxide to produce the radioactive drug product [C-11]LY2795050 ([C-11]PKAB). The product is purified by semi-preparative HPLC and formulated with a mixture of ethanol and saline (final ethanol concentration less than 10%). The final product solution is filtered through a 0.22 um membrane filter for terminal sterilization before its release for dispensing and IV administration.

The carbon-11 labeled drug product [C-11]LY2795050 ([C-11]PKAB) has a radioactive half-life of 20 min and has been demonstrated to be stable for at least 65 min after preparation and formulation. An expiration time of 60 min post-formulation will be assigned to the drug product.

For each batch of the radioactive drug product [C-11]LY2795050 ([C-11]PKAB) that will be used for human study, pyrogen and sterility tests will be performed. Pyrogen testing will be conducted in house at the Yale PET Center using FDA-approved method. Sterility test will be performed by the Yale Microbiology Laboratory.

The radioactive drug product [C-11]LY2795050 ([C-11]PKAB) will be produced according to the local Drug Master File and to local quality control procedures in effect at the Yale PET Center. Production of [C-11]LY2795050 ([C-11]PKAB) will be performed with the permission of Yale-New Haven Hospital RDRC

5. **Use of Placebo:** **Not applicable to this research project**

Provide a justification which addresses the following:

- Describe the safety and efficacy of other available therapies (if any).
This is not a treatment trial or a treatment seeking population of heavy drinkers
- State the maximum total length of time a participant may receive placebo while on the study.
No placebo
- Address the greatest potential harm that may come to a participant as a result of not receiving effective therapy (immediate or delayed onset.)
Not a treatment seeking population
- Describe the procedures that are in place to safeguard participants receiving placebo.

Not a treatment seeking population

6. Use of Controlled Substances:

Will this research project involve the use of controlled substances in human subjects?

Yes No See instructions to view controlled substance listings.

If yes, is the use of the controlled substance considered:

Therapeutic: The use of the controlled substance, within the context of the research, has the potential to benefit the research participant.

Non Therapeutic: Note, the use of a controlled substance in a non therapeutic research study involving human subjects may require that the investigator obtain a Laboratory Research License. Examples include controlled substances used for basic imaging, observation or biochemical studies or other non-therapeutic purposes. See Instructions for further information.

7. Continuation of Drug Therapy After Study Closure Not applicable to this project

Are subjects provided the opportunity to continue to receive the study drug(s) after the study has ended? Yes No

If yes, describe the conditions under which continued access to study drug(s) may apply as well as conditions for termination of such access.

SECTION VII: HUMAN SUBJECTS

1. Recruitment Procedures: Describe how potential subjects will be identified, contacted and recruited.

56 heavy drinkers, drinking on at least 4 days per week (20-45 weekly standard drinks for women and 25-70 for men), an equal number of family history positive and family history negative (as specified by the FHAM) will be recruited for the study. All subjects will be 21-65 years of age, physically healthy non-treatment-seeking heavy drinkers. Volunteers will be recruited through advertisements in local newspapers, postings in community locations (bars, coffee shops, grocery stores) and advertisements on free community TV channels. Additionally, 25 healthy controls who report drinking socially will be recruited to match the demographics and background of the heavy drinkers, including family history of alcoholism; these controls will be light social drinkers consuming less than or equal to 20 drinks per week for women, and less than 25 drinks per week for men in the past 90 days and not meet past or current criteria DSM-IV abuse or dependence criteria, for the past 5 years. The remainder of the exclusion criteria will be similar to the heavy drinkers.

1. Indicate recruitment methods below. Attach copies of any recruitment materials that will be used.

- | | | |
|--|--|---|
